Since endometriosis and fibroids are identifiable anatomical conditions but understanding of their mechanistic contribution to dysmenorrhea and bladder pain is limited, we will include confirmed endometriosis participants and fibroids participants mixed within our dysmenorrhea

cohort to determine which effects produced by the primary analysis are due to anatomical conditions.

Participants are divided into two arms. Arm #1 participants include women ages 18-45 with dysmenorrhea, women with painful bladder syndrome (PBS), and healthy controls. Arm #2 includes women ages 18-45 with chronic pain or special healthy controls.

Our hypotheses on mechanisms responsible for the transition of menstrual pain to bladder pain will be tested through the following phases:

Phase #1 (includes Arm #1 and Arm #2 participants): *To determine if dysmenorrhea with concomitant bladder pain sensitivity exhibits neurophysiological features consistent with established CPP.* Women with dysmenorrhea without COS and women with chronic pain conditions outside of the pelvic region will be used as controls. Quantitative sensory testing (QST) and a noninvasive bladder pain test we previously have validated will be used to determine whether impairments in descending inhibition and pelvic sensitivity are responsible for vulnerability to COS in women with dysmenorrhea (with and without COS) and/or CPP.

Phase #2 (includes a subset of Arm #1 participants only): *To differentiate the individual contributions of circulating sex hormones and repeated sensitizing events (painful menses) on descending and peripheral mechanisms of bladder pain.* The same QST/bladder pain measures studied in Phase #1 will be retested within the D+COS and PBS subjects following a one-year randomized trial of cyclical vs. continuous OCs vs. no treatment. We added a second option for those who are randomized to Phase 2 that did not want to commit to their randomized group. They will be asked to come in for an additional assessment visit a year later. Participating in the randomized group is preferable but this will allow us to still obtain the follow up data that is important with these participants even if they choose not to participate in their assigned group.

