Chronic pain participants will be allowed to skip portions of the assessment based on their pain conditions and will be enrolled using drastically different inclusion/exclusion criteria compared to other groups. We anticipate approximately 88 women with either dysmenorrhea or PBS to continue participation in the longitudinal study and trial of oral contraceptives for Phase 2. We expect approximately 50 women who were randomized will decide not to participate in phase 2 but will choose to come back in a year later for an additional assessment visit for long term follow up data. Our ultimate goal is to prevent and reverse COS. We will ask all subjects to complete an at home yearly follow-up questionnaire for 5 years (for participants who complete phase 2, the year 1 questionnaire will be incorporated into the 12-month testing Assessment #3 testing session). If our hypotheses are correct about descending inhibition impairments being reversible with OCs, our work will spawn prevention studies for other highly co-morbid conditions associated with dysmenorrhea such as headache and fibromyalgia.

C1: Phase 1 Methods

C1.a Study Participants: Reproductive-age women (age 18-45) with: ARM 1: a) dysmenorrhea, b) dysmenorrhea and bladder sensitivity (D+COS), c) painful bladder syndrome (PBS), d) healthy, pain-free controls, ARM 2: e) 10 “special” healthy control participants, and f) 50 chronic pain female patients.

Participants will primarily be recruited from NorthShore’s clinical sites in the Chicago-area. Participants may also be recruited from the community through advertising in NorthShore University HealthSystem’s outpatient clinics; web-based advertising; posters and flyers in local businesses (coffee shops, athletic clubs) and on college campuses; referrals from local gynecologists; and the Illinois Women’s Health Registry based at Northwestern University’s Feinberg School of Medicine. All flyers and ads will be IRB approved. In our ads, we will call the study CRAMPP (Chronic Risk Associated with Menstrual Pelvic Pain). Participants may call our research hotline directly or after they indicate interest and give permission, their doctor will send us their contact information and a research coordinator will call the patient to formally assess eligibility using a phone screen. At the end of the phone screen, adult participants will be asked if we have permission to put their phone screen and contact information into our recruitment registry.

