Adult Participants (arm #1 and arm #2) will complete the following questionnaires: a) complete medical, surgical, and gynecological history, and b) a psychosocial assessment using short-form PROMIS instruments (pain behavior, pain interference, fatigue, sleep, anxiety, depression, physical function, satisfaction with participation in social roles, and 10 item global health scale).³⁵ Participants will also complete the following pain rating questionnaires (the Interstitial Cystitis Problem and Symptom Indices, the Pain Catastrophizing Scale, Revised Short-form McGill Pain Inventory⁷² and MIDAS headache questionnaire).⁶⁷ These scales have been linked to pain intensity and quality of life in CPP sufferers, and catastrophizing (rumination, magnification, and feelings of helplessness about pain) is a well-validated intervention target for many cognitive-behavioral approaches for chronic pain.³⁶⁻³⁹ Validated, CPP-specific assessment tools will be used to characterize IBS (Rome III criteria)⁴⁰ and PBS symptoms (Genitourinary Pain Index).⁴¹ Subjects will also complete the Female Sexual Function Index (FSFI)⁶⁸ and BSI-18 based questionnaire containing 6 somatization questions selected from the BSI-18⁶⁹ plus a vision question, and the Complex Medical Symptoms Inventory (CMSI)-General, Fibromyalgia Symptoms, Fatigue, and Vulvodynia sections.^{70,71} All questionnaires will be collected electronically using REDCap.

Note that midway through the study, an amendment was made for arm #1 and arm #2 study participants were freed from the requirement to undergo a complete gynecologic exam during the screen visit and as part of phase 1 participation. Instead, only arm #1 painful bladder syndrome and D+COS participants who randomize into phase 2 and agree to participate in phase 2 will be required to undergo a complete gynecological exam. These participants will be required to complete the gynecological exam at some point before their first phase 2 assessment visit (i.e. Assessment Visit #2 - 6 month visit). Transvaginal ultrasound and/or abdominal ultrasound may be performed on dysmenorrhea participants whose exam and/or history is suggestive of ovarian or uterine masses. Arm #1 PBS participants may choose to complete the gynecological exam during their screen visit if they prefer since their randomization to phase 2 is already determined.

Even though a gynecological exam is no longer required for phase #1, the second phase 1 visit

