(assessment visit #1) includes internal vaginal pressure-pain threshold testing, which is similar in nature to the pelvic floor portion of a gynecological exam. Thus, for participants who have never had a gynecological exam, a study nurse or study doctor may complete a simple exam of the pelvic floor at the screen to promote understanding of the internal vaginal pressure-pain threshold testing that will be completed at the assessment. This ensures that the integrity of our data is not biased by unfamiliar experience. Participants will be asked whether they have ever had a gynecological exam on the phone screen and a simple exam of the pelvic floor for those that say they have never had an exam will be scheduled into their screen.

Participants entering phase 2 will still need to complete a birth control pill medical screen checklist in person or over the phone with a study doctor or study nurse before the pills can be prescribed.

Note arm #1 participants who indicate on a phone screen that they are unwilling to undergo gynecological exam will remain ineligible for the study since the assessment visit involves internal vaginal testing, which is similar in nature to an exam, and because our ultimate goal is to identify participants who will be eligible for phase 2, which requires a gynecological exam. However, participants enrolled in arm 2 with chronic pain who are unable to tolerate the internal testing may still skip this procedure.

Participants will be asked to do a tampon test originally designed to study vulvodynia.⁴² The tampon test may be performed by the participant during the visit or at home. The tampon test is a standard test in which subjects report the amount of pain they feel on a 0-10 numerical rating scale after inserting a standardized tampon (Tampax original regular with plastic applicator, Proctor and Gamble).

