collected electronically using REDCap at home. If requested, paper versions can be provided instead and mailed in. For participants continuing to Phase 2, the year 1 annual medical history questionnaire will usually take place during their assessment #3 visit. All participants that complete phase 1 (Screen + Assessment #1), including phase 2 dropouts, will be asked to complete the annual follow-up questionnaire.

Group (Sample Size)	H (20)	D (20)	D+COS (95)	PBS (40)	P (50)	MSA
Bladder Pain at FU (VAS)	0	0	2.5	3.0	-	0.85
Pelvic Hyperalgesia (VAS)	0	0	3	3	-	0.84
Pelvic Hyperalgesia (Time)	0	0	2	2.5	-	0.83
Pelvic Pain Thresholds	0	.5	.5	2.3	-	0.81
Bodily Pain Thresholds	0	1.5	2	2	2.3	0.91
Conditioned Pain Modulation	0	1-2	1-2	4 _a	2-4 _b	0.94
Menstrual Pain History	0	3.7	5	6	-	0.81
Temporal Summation	0	0	.7	.8	-	-
Estradiol	0	1-3 _c	1-3 _c	1-3	-	0.84
Depression/Anxiety	0	.3	.4	2	2-4	0.82

Table X: Sample sizes and hypothesized results in Z-scores or range of Z-scores (relative to healthy) for subjects that are healthy (H), have dysmenorrhea (D), have cross organ sensitization (D+COS), PBS, or chronic pain (P). MSA indicates Kaiser's measure of sampling adequacy. Numbers in italics indicated minimum detectable hypothesized score with current sample size. Z-scores based on preliminary data, or others indicated by subscript (a: ⁹, b: ^{11,13}). Effects temporal summation in these populations are unknown, but effect sizes as large as 1.1 have been reported for fibromyalgia. Dashes (-) indicate unknown effect size.

C1.h Data Analysis/Sample Size Requirements: The primary outcomes under this hypothesis will be [1] bladder pain at FU, [2] pelvic hyperalgesia (VAS, time to return to baseline pain), reflecting peripheral dysfunction/sensitization, and [3] centrally mediated hyperalgesia (CPM, bodily pain thresholds).

Factor [1], Bladder pain at FU: Our preliminary data on healthy subjects and women with dysmenorrhea, in combination with other studies investigating migraine and PBS, suggests effect sizes between 1.4-5.6 (Cohen's d). As a control comparison, we expect that women with chronic pain will have levels of bladder and pelvic sensitivity comparable to healthy subjects. We will perform t-tests for each of these three pain variables using pairwise contrasts and appropriate Bonferroni corrections for six group comparisons.

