C1.j Potential Problems: *Primary and/or secondary comparisons are nonsignificant: a mixture of mechanisms are involved in D+COS phenotype or PBS.* We will confirm whether our paradigm was sufficient to detect deficits in CPM using our positive control group with chronic pain to validate a true negative finding. Afterwards, we will use cluster analyses to identify phenotype patterns and confirm mechanistic differences with banked serum. *Why not examine additional hormones?* We are examining hormones that have been frequently studied in pain research and will bank serum allowing for the future possibility of studying others. *What about endometriosis, fibroids and other known anatomic uterine pain conditions?* To account for the common conditions (especially within our medical practice), we will include 10 confirmed endometriosis (operative report review) participants and 10 fibroids participants (ultrasound or surgical confirmation) mixed within our dysmenorrhea cohort to determine which effects produced by the primary analysis are due to anatomical conditions.

C2. Methods for Phase #2

C2.a Participation criteria

All phase #1 participants with D+COS (pool of 95 candidates) or PBS (pool of 40) will be enrolled with intent to transition into phase #2, though the second phase of the study will be presented as optional. If they choose not to participate in their randomized group, they will have the option to come back in a year later for an additional assessment visit for long term follow up data. These enrollment targets, accounting for a potential 35% dropout rate, will enroll 62 participants with D+COS and 26 PBS. This will provide adequate power for the prespecified contrasts.

Inclusion Criteria: 1) Participation in Phase #1 and assigned to the Arm #1 PBS or D+COS group, 2) willing to comply with OC assignment (continuous for PBS; cyclical, continuous, or no OC for D+COS).

Exclusion Criteria: a) presence of active pelvic or abdominal malignancies (primary or metastatic), b) absence of regular menses (including current pregnancy, recent pregnancy, or active breast feeding), c) unwilling to undergo pelvic examination/testing, e) standard contraindications to use of OCs:

- Thrombophlebitis or thromboembolic disorders, or a history thereof
- Cerebrovascular or coronary heart disease
- Known or suspected carcinoma of the breast
- Endometrial cancer or other known or suspected estrogen-dependent neoplasia
- Undiagnosed abnormal genital bleeding

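### Phase 2: D+COS women may decline their randomised arm once they know it, and the posted plan gives no comparison by assigned arm (Z1, Z2, Z4) to support its randomised-trial claim

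*Combined protocol and SAP*

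**What the plan says.** **Allocation and refusal.** C2.b and C2.c randomise D+COS women to cyclical OC, continuous OC or no OC (26, 26 and 10) and state that participants cannot be blinded. Section A adds: "We added a second option for those who are randomized to Phase 2 that did not want to commit to their randomized group". B.1 puts a number on it: "We expect approximately 50 women who were randomized will decide not to participate in phase 2", against about 88 who continue. C1.b likewise separates women who are randomised from those who then accept, requiring a gynaecological exam only of PBS women and of "D+COS participants who randomize into phase 2 and agree to participate in phase 2". Yet C2.a makes it an inclusion criterion to be "willing to comply with OC assignment (continuous for PBS; cyclical, continuous, or no OC for D+COS".

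**Follow-up of decliners.** Section A says "They will be asked to come in for an additional assessment visit a year later". C2.d makes the same visit only a possibility. No 6-month visit is described for them. C1.g says all who complete Phase 1, "including phase 2 dropouts, will be asked to complete the annual follow-up questionnaire".

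**Analyses.** C2.a sizes Phase 2 by "accounting for a potential 35% dropout rate, will enroll 62 participants with D+COS and 26 PBS", and Table z carries these counts before and after attrition. Z1 tests change in bladder pain at 6 months, with 12 months as confirmation; Z2 and Z4 use both time points. None of the three defines an analysis set or mentions decliners. Z1 and Z2 describe their contrasts by OC use. C2.g and C2.j apply intent-to-treat wording only to women withdrawn from, or stopping, OCs; C2.g says they might be asked back, and also names them a separate comparison group. C2.j accounts for every treatment deviation as a covariate, naming no model. Z1 also adjusts for E2 and P4.

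**The concern.** Randomisation makes the arms comparable at the moment of allocation. If women can leave after learning their arm, and only those who stay are analysed, that holds only when the same kind of woman leaves each arm at the same rate. Equal refusal rates are not enough: women who refuse continuous OCs need not resemble women who refuse no treatment. Stable differences in pain level largely cancel in a test against baseline, but selection on how pain changes does not.

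Adjusting for deviations is a related but lesser hazard. Extra OC pills for bleeding, the plan's own example, cannot occur in the no-OC arm. Conditioning on such an event can distort the arm contrast if it also depends on pain.

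At stake is C2.i's statement that Phase 2 will supply prospective randomised-trial evidence that bladder pain sensitivity can be modified. That needs an estimate by assigned arm.

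**Working it through.** **1. The plan's own figures.** Z4 has d=0.8, α=0.05 (two-sided assumed) and power 0.80. The two-sample t-test needs 25.5, so 26 per arm, total 52, with power 80.7%. This matches Table z. Attrition also matches: 80×0.65=52, 95×0.65=61.75 (62), 40×0.65=26.

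**2. Where decliners seem to sit.** After attrition, 62+26=88, the number B.1 expects to take part. This suggests that the analyses are sized on women who accept their arm. It is not proof: 88+50=138 exceeds the pool of 95+40=135, the 50 are not split by group, and the 35% is described as dropout.

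**3. Bias if decliners are left out (assumed inputs).** Let a share p decline and let decliners differ from acceptors by g SD in pain change, in one arm only. Bias = p×g. Here p=0.35 is borrowed from the dropout allowance. Type I error is from the noncentral t, two-sided 5%, with no true effect:

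| g (SD) | bias (SD) | 26 v 26 (Z4) | 52 v 10 (Z1 layout) |
|---|---|---|---|
| 0 | 0 | 5.0% | 5.0% |
| 0.25 | 0.35×0.25=0.09 | 6.1% | 5.7% |
| 0.5 | 0.35×0.5=0.18 | 9.5% | 7.9% |
| 1 | 0.35×1=0.35 | 23.6% | 16.9% |

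If selection is the same in both arms, bias = (difference in refusal)×g. Refusal of 25% v 45% with g=0.5 to 1 gives 0.10 to 0.20 SD and 6.4% to 10.9% at 26 v 26. With equal refusal as well, bias is zero.

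**4. Deviation covariate (simulated).** Settings: 26 per arm, no arm effect, probability of deviating logistic in arm and pain change, model change ~ arm + deviation.
- 5% v 10% deviating, odds ratio 3 per SD of change: bias about 0.05 SD, type I error 5–6%.
- 20% v 40%, odds ratio 3: 0.18 SD, 10.2%.
- 30% in both arms with the same link to pain: no bias, about 5%.

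**5. What a by-assigned-arm estimate would cost Z4.** Take 40 v 40 (Table z's 80 before attrition), 35% declining and all returning.
- Decliners keep none of the effect: d=0.8×0.65=0.52, power 63%.
- They keep half: d=0.8×0.825=0.66, power 83%.
- Compare 81% at 26 v 26 with d=0.8.

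**6. Partial return.** If a random share r of decliners returns, the remaining bias is g×[0.35 − 0.35r/(0.65+0.35r)]. For g=1 this is 0.14 SD at r=0.5, 0.05 SD at r=0.8 and 0 at r=1.

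**The case against.** The strongest reply is that decliners are simply outside Phase 2. Willingness to comply is an inclusion criterion, B.1 says these women do not participate in Phase 2, their visit is described as long-term follow-up, and C2.h introduces Z1–Z5 as the analyses that complete Phase 2. That is the natural reading, but it confirms the problem: exclusion follows randomisation and knowledge of the arm.

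Other objections limit the claim, and they stand:
- The 35% is a dropout allowance, which Z1 benchmarks against published rates of 18–24%. No refusal rate is given for D+COS women. A reader might infer that over a third of them refuse, from 50 against 88; the documents do not support that, because PBS women, who have only one regimen, may be among the 50. Phase 2 is also optional, so some may refuse it whatever their arm.
- C2.c can be read as randomising 62 D+COS women, not 95, so the 40 v 40 base is itself an assumption.
- C2.j concerns differences within groups, partly PBS medication changes outside the randomised contrast. C2.c and C2.g describe breakthrough bleeding as minimal or uncommon, so high deviation rates are hard to assume.
- The two labels in C2.g need not conflict; they can mean two analyses.
- The posted text is edited and cites sections that are not posted. An analysis-set definition could be there, but it does not help a reader of the posted plan.

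**Conclusion.** The point holds for the posted plan. Randomised, unblinded D+COS women may refuse their arm, decliners appear to be left out of Z1, Z2 and Z4, and no estimate by assigned arm supports the randomised-trial claim. It should be fixed; confidence is medium.

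A reader might infer that the OC comparison is biased, or that its type I error is 23.6%. Neither follows. Refusal by arm and decliners' outcomes are not given, so size and direction are unknown, and the top figure needs a 1 SD difference confined to one arm. Nor does the plan clearly commit to analysis by treatment taken: the wording of Z1 and Z2 fits either assigned arm or actual use. The deviation covariate is minor unless deviations are common and unequal between arms. The E2/P4 adjustment is only ambiguous, since it asks a mediation question and may be a second step. Z3 (one regimen) and Z5 (groups defined by outcome) are not affected in this way.

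**What to change.** (a) For Z1, Z2 and Z4, add a 12-month estimate on all randomised D+COS women by assigned arm, using the visit already planned for decliners and stoppers. Reconcile Section A with C2.d and C2.g so that all of them are asked back. Keep the 6-month Z1 test, labelled as covering women who accepted their arm, and rest any randomised-trial claim on the by-assigned-arm estimate.

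(b) Use only baseline covariates in the main Z1, Z2 and Z4 models. Move treatment deviations to a sensitivity analysis, and report the E2/P4-adjusted Z1 model as a mediation analysis beside the unadjusted one.

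(c) Report refusal, and the baseline characteristics of decliners and acceptors, by arm. Refusal rates alone could reassure falsely.

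Cost: mainly protocol and analysis wording, with no new type of visit. The added estimate is diluted, with the Z4 power range shown above, and power would be lower still if only 62 women are randomised. It also depends on decliners returning: if return itself depends on pain change, some bias remains.
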